### 9.2 Study Design

Patients with histologic confirmation of invasive adenocarcinoma of the breast will be randomized according to the permuted block algorithm with a 1:1 randomization ratio to arms A and B. Stratification factors include:

- Setting in which patient developed resistance to prior non steroidal AI treatment (adjuvant vs. metastatic)
- Geographic region (USA vs. other)
- Visceral disease (yes vs. no)
- Prior fulvestrant use (yes vs. no)

**NOTE:** Visceral disease is defined as lung and/or liver involvement.

Taking into consideration the accrual rates of the BOLERO-2 study (40 patients/month, 700 patients over 18 months with 24 international sites), the ENCORE 301 study (5 patients/month, 130 patients over 2 years at 38 sites US and international) and the CONFIRM study (24 patients/month at 128 sites), all of which have been conducted in the AI refractory setting, and the 1st line SWOG

S0226 study (10 patients/month, 700 patients over 6 years), we anticipate an accrual rate of approximately 15 patients per month in our study.

Enrollment of 600 patients will be required to provide adequate power for the OS endpoint (see Section [9.2.2](#)). The first 360 patients will be used for the primary evaluation of PFS (see Section [9.2.1](#)), objective response rate (ORR), toxicity, time to treatment deterioration and patient-reported outcomes. If the PFS analysis is positive, the data for first 360 patients would be used for a submission to the FDA. At the time of final analysis for the OS endpoint, secondary analyses of PFS, objective response and toxicity will be conducted in all 600 patients, along with the primary analyses for the pharmacodynamic acetylation marker data and adherence to protocol therapy data. Imaging studies for all 600 participants will be collected and archived at the ACR Imaging Core Laboratory.

For purposes of comparability to the phase 3 study of exemestane in advanced breast cancer patients by Chia et al., enrollment in this study will attempt to achieve a target patient population that consists of approximately 80% of patients having measurable disease (with at least 1 measurable lesion at baseline assessment and identification of up to 5 total target lesions [maximum of 2 lesions per organ] and 5 total non-target lesions) and approximately 20% of patients having non-measurable disease only.

No early stopping for efficacy based on PFS will be considered in the study so that there will be sufficient death events for OS comparison in the final analysis. Hence, for PFS, the study will only be monitored for early stopping for futility. Interim analyses of OS will start at about 30 months (24 months of accrual + 6 months of data collection and cleaning) after study activation. Details about interim analysis for PFS and OS are described in Section [9.2.3](#).

#### 9.2.1 Sample size and accrual for PFS

For patients with HR-positive, HER2-negative MBC, the median PFS on the Exemestane + Placebo arm will be about 4.1 months in AI refractory setting based on BOLERO-2 central assessment results. The null hypothesis is hazard ratio (HR)=1 for comparison of PFS in the two treatment arms, and the alternative hypothesis is HR=0.58 for arms A/B. The primary analysis of PFS will be performed using a stratified log-rank test, with one-sided type I error of 0.1%, stratifying on randomization stratification factors. The primary comparisons will be intention-to-treat analysis (defining groups by assigned treatment regardless of treatment received) among all refractory patients regardless of eligibility status. A total accrual of 360 patients and total information of 247 PFS failures is planned, to give 88.5% power to detect a 42% reduction in the PFS failure hazard rate with no interim efficacy analysis. This difference corresponds to an improvement in median PFS from 4.1 to 7.1 months (i.e., 3.0 months of benefit), under the assumption of exponential distribution of PFS. Assuming an accrual rate of 15 patients per month, about 24 months of accrual will be needed without additional follow up to reach the expected number of PFS events.

The data for the primary analysis for the PFS comparison is expected to be available at about 30 months (24 months of accrual + 6 months of data collection and cleaning) after study activation, when the first

interim analysis for OS will be conducted. When to release the PFS data, however, depends on the result for the first interim analysis of OS. If the OS interim analysis is positive (ie, crossing the efficacy boundary listed in Table 9.2, see Section [9.2.3](#)) at the final PFS analysis time, the whole study will be stopped early for efficacy and the results for both PFS and OS will be released to Syndax and the public. If OS does not cross the efficacy boundary, in order to minimize the potential effect of releasing PFS result on the OS endpoint, the results of primary analysis for PFS will be held by the ECOG-ACRIN study statistician and the ECOG-ACRIN Data Safety Monitoring Committee (DSMC) members and not released to Syndax, CTEP, the principal investigators, anyone at ECOG-ACRIN involved in the day-to-day running of the trial or publically until all 600 patients required for the OS endpoint have been accrued for the whole trial (expected to occur at about 40 months after study activation, see Section [9.2.2](#)). In this case, the primary analysis of PFS will use follow-up through the calendar time of the 247th PFS event among the first 360 patients enrolled, even though more follow-up is expected to be available at that time (ie, completion of accrual). After completion of overall study accrual, the PFS results will be released to Syndax and may be released publically if allowed by the ECOG-ACRIN DSMC.

#### 9.2.2 Sample size and accrual for OS

Taking into consideration the median OS in the ENCORE 301 trial (20 months in the Exemestane + Placebo arm and 28 months in the entinostat arm) and the CONFIRM 2 trial (25.1 months in the high dose fulvestrant arm and 22.8 months in the low dose arm), it is expected that the median OS for patients on the Exemestane + Placebo arm will be about 22 months in the AI refractory patients. The null hypothesis for the OS comparison is  $HR=1$ , and the alternative hypothesis is  $HR=0.75$  for arms A/B. The primary analysis of OS will be performed using a stratified log-rank test, with one-sided type I error of 2.4%, stratifying on randomization stratification factors. The primary comparisons will be intention-to-treat analysis among all refractory patients regardless of eligibility status. A total accrual of 600 patients and total information of 410 OS failures is planned to give 80% power to detect a 25% reduction in the OS failure hazard rate with interim analysis plan described in Section [9.2.3](#) (Table 9.2). This difference corresponds to an improvement in median OS from 22 to 29.3 months (i.e., 7.3 months of benefit), under the assumption of exponential distribution of OS. Assuming an accrual rate of 15 patients per month, about 40 months of accrual will be needed with additional 24 months of follow up to reach the expected number of OS events. The final analysis for the OS comparison is expected to occur at about 70 months (40 months of accrual + 24 months of follow up + 6 months of data collection and cleaning) after study activation.

### **Interim futility analysis for PFS tests**

As mentioned above, in order to ensure sufficient sample size for OS comparison, no early stopping for efficacy based on PFS is considered in the study, and the study will only be monitored for early stopping in favor of the null hypothesis for PFS tests (i.e., futility) by the ECOG-ACRIN DSMC via its semi-annual DSMC meetings.

We adopt the general inefficacy interim monitoring method (described in the paper by Freidlin, Korn and Gray, *Clinical Trials*, 2010, which is called Linear 20% Inefficacy Boundary method) for futility monitoring in the study. This method generally results in less than 1% loss of power, there will be no sample size increase to account for the futility monitoring in the study.

Before interim analysis using the Linear 20% Inefficacy Boundary method, we will first perform a “harm” look at 25% information (about 9.5 months after study activation), using the rule that stops the trial for harm if the one-sided lower 95% unadjusted confidence bound for the observed hazard ratio (HR) is above 1 (i.e.,  $HR > 1.52$ ). This is the same as one-sided 0.05 level test of the null hypothesis in the direction of harm. If the trial does not stop at the “harm” look, the study will be monitored by formal interim analysis via Linear 20% Inefficacy Boundary method as described below. If the study stops at the “harm” look, the whole trial stops for lack of efficacy.

The one-sided type I error is 0.1% and the power is 88.5% for the PFS test, the first interim analysis could take place at as early as 21% information time per the Linear 20% Inefficacy Boundary method, at which the observed hazard ratio  $> 1$  would imply that the two-sided 95% confidence interval for log hazard ratio would not contain the  $\log(0.58)$ . Since the “harm” look will take place at 25% information time, and a 10% increment in information time is suggested for interim futility analysis by the method, the first interim analysis will be performed at the first DSMC meeting when at least 35% of the total information has been reported. Since 247 PFS events are required as the total information under the alternative hypothesis, the first interim analysis for futility is estimated to take place after 87 PFS events have occurred, which corresponds to 11.5 months after activation of the study in calendar time, under the accrual and failure rate assumptions mentioned above. Interim analysis will be performed for each subsequent DSMC meeting until either the criteria for early stopping (described below) are met or the total planned number of PFS events has been reported. In total, this design is expected to incorporate 2 interim analyses and one final analysis for PFS comparisons. The cut-off values for HRs and lower two-sided 95% confidence interval bound (unadjusted) are given in Table 9.1. If at any time point, the observed hazard ratio (arms A/B) is larger than the cut off values, the trial will stop in refractory setting for lack of efficacy.

In each interim analysis, the observed hazard ratio will be calculated using stratified Cox proportional-hazards model, stratified on randomization stratification factors, without any other covariates.

Because interim analyses are timed to coincide with the semi-annual ECOG-ACRIN DSMC meetings, the boundaries for HRs may change depending on the number of observed PFS events at that time. Also, because of delays in data submission and processing, it is likely that actual analysis times will be 6-12 months later.

**Table 9.1: Inefficacy stopping boundaries for PFS endpoint (Alternative HR=0.58, Full information=247 PFS events, Type I error=0.1%, Power=88.5%)**

Repeated interim futility analysis	1	2
Information time	35%	65%
Calendar time (months after study activation)	11.5	17.5
Hazard ratio (stopping boundaries)	0.981	0.941
Lower two-sided 95% confidence bound (unadjusted, Z=1.96 at all interim looks)	0.643	0.691

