The ENCORE 301 randomized phase 2 study evaluated the role of entinostat, a class 1 selective HDAC inhibitor, in combination with exemestane (steroidal AI) in the advanced breast cancer setting. Postmenopausal women who had received  $\leq 1$  prior chemotherapy and were progressing on a non-steroidal AI were randomized to exemestane 25 mg daily plus entinostat 5 mg weekly versus exemestane plus placebo weekly. A significant improvement in PFS was noted in the entinostat arm versus placebo (median 4.3 versus 2.3 months, respectively). In an exploratory analysis of patients who were deemed resistant to prior AI, patients randomized to the entinostat arm had a greater PFS than those in the placebo arm. OS, an exploratory endpoint, was also significantly longer in the entinostat arm versus the placebo arm (28.1 versus 19.8 months, respectively). Interestingly, in a subset analysis examining protein acetylation in entinostat patients (n=27), the median PFS increased to 8.5 months in those exhibiting protein lysine hyperacetylation, and this was apparent after just 2 weeks of therapy. The addition of entinostat to AI therapy may delay the initiation of subsequent therapies such as chemotherapy by prolonging PFS on exemestane. We propose to evaluate the addition of entinostat or placebo to exemestane in patients who have progressed on a non-steroidal AI. In addition, we will explore whether benefit varies with changes in lysine acetylation.

Rev.10/15 **Table 1.1: Select Clinical Trials of Novel Combinations with Endocrine Therapy in Metastatic Breast Cancer**

Clinical Trial	Treatment Arms	Patient Population	Results
ENCORE Phase 2 Trial 	Exemestane + Entinostat/Placebo 5mg po weekly	Postmenopausal women Prior progression on a non-steroidal AI and $\leq 1$ prior chemotherapy	Median PFS 4.3 (entinostat) versus 2.3 months (placebo); HR 0.73 Median OS 28.1 (entinostat) versus 19.8 months (placebo); HR 0.59
Rev. 4/15 ECOG-ACRIN Phase 3 Trial ([name])	Exemestane + Entinostat/Placebo 5 mg po weekly	Pre/perimenopausal and post-menopausal women and men HR-positive advanced breast cancer Prior progression on a non-steroidal AI (adjuvant/metastatic) and $\leq 1$ prior chemotherapy for metastatic disease	Pending
BOLERO-2 Phase 3 Trial 	Exemestane + Everolimus/Placebo	Postmenopausal women Prior progression on a non-steroidal AI and $\leq 1$ prior chemotherapy	Median PFS 7.8 (everolimus) vs 3.2 (placebo) months

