#### 1.4 Study Rationale

Despite advances in the treatment of patients with ER-positive breast cancer, many women fail to respond to an AI or suffer recurrence of disease notwithstanding optimal adjuvant therapy. Patients with advanced stage ER-positive breast cancer have a median survival of approximately 18-24 months and in this setting hormonal therapy provided a 20-30% response rate and a 9-11 month PFS. Tumors may be intrinsically (de novo) resistant to hormonal therapy and will therefore never respond to an AI, or they may acquire resistance at a

later time-point through various host or tumor-mediated mechanisms. Women with hormone receptor-positive metastatic breast cancer receiving hormonal therapy are also subject to drug resistance. Clearly strategies to overcome resistance to hormonal agents are urgently required in an effort to improve outcomes for breast cancer patients and delay the time to chemotherapy use.

A variety of resistance mechanisms have been shown to occur in tumor cells resistant to AIs, including loss of ER expression, activated growth factor signaling pathways, estrogen independent tumor growth, hypersensitivity of tumor cells to low estrogen concentrations and cyclin D1 over-expression. Targeting these mechanisms would be expected to restore sensitivity to AIs and increase both the number of patients that respond as well as prevent or delay the time to progression on AI therapy. HDAC inhibitors are one class of compounds that have been shown to inhibit many of the AI resistance pathways pre-clinically.

Pre-clinically, entinostat has been shown to induce protein lysine acetylation, resulting in down-regulation of estrogen-independent growth factor signaling pathways and normalization of ER levels. In addition, there is a suggestion that entinostat may have longer term effects on cancer phenotypes, cancer stem cell or progenitor cell pool and potentially sensitization to subsequent post-study treatments. In a recently reported randomized phase II trial, the addition of entinostat to exemestane improved PFS and OS in patients with previously treated hormone-sensitive metastatic breast cancer. Pharmacodynamic analysis in a subset of patients links HDAC inhibitor activity to breast cancer clinical outcome. A phase II biomarker validation study is being planned to further delineate the role of entinostat and the potential biomarker of lysine acetylation in this setting (refractory to non-steroidal AI).

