## 9. Statistical Considerations

### 9.1 Study Objectives

Rev.10/15

The primary objective of this randomized, placebo-controlled, double-blinded, phase III study is to determine whether Exemestane + Entinostat (Arm A) improves progression-free survival (PFS) and/or overall survival (OS) compared to the Exemestane + Placebo (Arm B) in patients with hormone receptor-positive, human epidermal growth factor receptor 2 (HER2)-negative locally advanced or metastatic breast cancer (MBC) who have experienced disease progression after non-steroidal AI use in the adjuvant setting (within 12 months prior to enrollment) or in the metastatic setting.

Both PFS and OS are primary endpoints, and the study is designed to show an improvement in either PFS or OS. PFS is defined to be time from randomization to the earliest of documented disease progression as defined by the Response Evaluation Criteria In Solid Tumors (RECIST) 1.1 criteria, new primary breast cancer, or death without progression. Disease assessment will continue until disease progression, even after non-protocol anti-cancer therapy is started. Cases with incomplete follow up or without adequate disease evaluations will be censored at the date last documented to be free of progression, regardless of whether non-protocol anti-cancer therapy is started or not. Tumor response and progression will be defined by central review, including time point-by-time point radiologist reader review at the ACR Imaging Core Lab for patients with radiographically measurable/evaluable disease, and/or an independent review committee for patients with measurable/non-measurable disease that is not radiographically evident (i.e., skin lesions). OS is defined to be time from randomization to death from any cause, censoring cases who had not died at the date last known alive.

This study is aimed to give adequate power for both PFS and OS comparisons. The one-sided type I error of 0.025 is split between two hypotheses tests to control the overall type I error rate for the whole trial. Specifically, type I error rate is 0.001 for PFS test and 0.024 for OS test.

Rev.10/15

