#### Interim analysis for OS tests

Regardless of PFS results, the first interim analysis of OS will be performed at the final PFS analysis time (expected to be 24 months after study activation-see Section [9.2.1](#)). Interim analysis for OS will then be performed biannually until either the criteria for early stopping (described below) are met or the total planned number of OS events has been reported. Of note, interim analyses will be skipped if the change in the information since the previous interim analysis is less than 10%. In addition, when the information time reaches 90% or more, interim analysis will not be conducted, and the final analysis of OS will be performed when full information is reached. These interim analyses will be monitored by ECOG-ACRIN DSMC. Table 9.2 shows the operating characteristics for OS endpoint.

At each interim analysis, the stratified log rank test statistic will be computed. To preserve the overall one-sided type I error rate at 2.4% for the OS endpoint, critical values for rejecting null hypothesis at the interim analyses will be determined using a truncated version of the Lan-DeMets spending function corresponding to the O'Brien-Fleming boundary (1979). If the boundary is crossed at an interim analysis or at the final analysis, then the null hypothesis will be rejected, and the Exemestane + Entinostat therapy is superior to the exemestane monotherapy in terms of OS. If the criteria for rejecting the null hypothesis are not met, then it will be concluded that this trial fails to show superiority of Exemestane + Entinostat therapy over the exemestane monotherapy on OS.

Because interim analyses are timed to coincide with the ECOG-ACRIN DSMC meetings, these boundaries may change depending on the number of observed OS events at that time. Also, because of

delays in data submission and processing, it is likely that actual analysis times will be 6-12 months later.

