**Table 9.2: Operating Characteristics for OS Endpoint**

Repeated Analysis	Real time (months)	Information time	Failures under alternative hypothesis	Nominal significance (one-sided)	Upper boundary
1	24	0.24	101	0.00048	3.3020
2	30	0.36	149	0.00048	3.3020
3	36	0.49	203	0.00068	3.2036
4	42	0.64	261	0.00400	2.6518
5	48	0.76	313	0.00805	2.4065
6	54	0.87	355	0.01193	2.2593
Final	64	1.00	410	0.01872	2.0808

If PFS test is negative in the primary analysis, this study will also be monitored for early stopping in favor of the null hypothesis (i.e., futility) for the OS test using the Jennison-Turnbull repeated confidence interval (RCI) method. At each interim OS analysis, the RCI on the observed hazard ratio will be computed using the critical values from the above error spending rate function. If the RCI does not include the alternative hazard ratio of 1.33 (arms B/A), then the OS comparison would be stopped early for lack of benefit. The observed hazard ratio will be calculated using stratified Cox proportional-hazards model, stratified on randomization stratification factors, without any other covariates. If the PFS test is positive in the primary analysis, no interim futility analysis for OS will be conducted.

As mentioned in Section 9.2.1, if the first interim analysis of OS is positive, the interim OS data will be released to Syndax and the public and the study will be stopped early for efficacy. If the first interim analysis of OS does not cross the efficacy boundary, then at the time study accrual is completed, if (1) the primary PFS test is positive at the 0.001 level, and (2) the estimated PFS hazard ratio for Exemestane + Entinostat vs. Exemestane + Placebo is  $< 0.675$ , the interim OS data will also be confidentially released to Syndax. The DSMC will also be asked to allow use of interim OS data from the first 360 patients enrolled in an application to the FDA, with the understanding that the data not be made public unless required as part of the FDA review process.

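### Does the interim PFS futility rule wrongly close the OS comparison before OS has been looked at?

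*Combined protocol and SAP*

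**What the plan says.** Section 9.1 sets up two routes to success: "Both PFS and OS are primary endpoints, and the study is designed to show an improvement in either PFS or OS". The one-sided alpha of 0.025 is split unevenly: "type I error rate is 0.001 for PFS test and 0.024 for OS test".

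Section 9.2.3 (Interim futility analysis for PFS tests) applies the Linear 20% Inefficacy Boundary to PFS. Table 9.1 gives cut-offs of 0.981 at 35% information (87 events) and 0.941 at 65% (65% of 247, or 161 events), after a harm look at 25%. If the observed ratio "is larger than the cut off values, the trial will stop in refractory setting for lack of efficacy". Nothing there makes the rule advisory or lets OS continue. The words about a refractory setting mark out no subset, because Sections 9.2.1 and 9.2.2 analyse all refractory patients; they are a clerical leftover.

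Once PFS reaches its final analysis the logic changes. In Interim analysis for OS tests: "Regardless of PFS results, the first interim analysis of OS will be performed at the final PFS analysis time". Under Table 9.2: "If PFS test is negative in the primary analysis, this study will also be monitored for early stopping". That OS monitoring uses a repeated confidence interval on the OS hazard ratio, not PFS.

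**The concern.** The two branches seem to treat the same evidence in opposite ways. A PFS ratio of 0.95 at 161 events closes OS. The same 0.95 at 247 events is firmer evidence against a PFS benefit, yet OS carries on towards 410 deaths. The plan thus accepts that OS might improve without PFS, but only if PFS has first survived two early looks that use no OS data.

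The background makes this more than theoretical. Section 1.4 mentions "potentially sensitization to subsequent post-study treatments". Table 1.1 reports "Median PFS 4.3 (entinostat) versus 2.3 months (placebo); HR 0.73" and "Median OS 28.1 (entinostat) versus 19.8 months (placebo); HR 0.59", so the phase 2 survival effect was the larger one. The PFS boundary is calibrated to 0.58, a stronger effect than phase 2 showed. If the truth were nearer 0.73, PFS would probably miss its 0.001 level and OS would be the main route to a positive trial. An interim stop would then leave the endpoint holding 96% of the alpha (0.024/0.025) untested.

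**Working it through.** **Inputs.** From the plan: 247 PFS events, PFS alternative 0.58, one-sided 0.001; 410 deaths, OS alternative 0.75, one-sided 0.024; 15 patients per month; control medians 4.1 and 22 months; phase 2 ratios 0.73 and 0.59. With 1:1 allocation the variance of a log hazard ratio is taken as 4/d for d events.

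**The plan's own figures reproduce.**
- PFS power: Φ(√(247/4) × ln(1/0.58) − 3.09) = 88.3% (stated 88.5%).
- Boundary: the log cut-off falls linearly from 0 at 21% information to 0.2 × ln(0.58) at 100%. This gives 0.981 at 35% and 0.941 at 65%, as in Table 9.1.
- Harm cut-off: exp(1.645 × 2/√(0.25 × 247)) = 1.52, as stated.

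**The asymmetry.** The 95% interval is HR × exp(±1.96 × 2/√d).
- 0.95 at 161 events: 0.70 to 1.29. It exceeds 0.941, so the trial stops.
- 0.95 at 247 events: 0.74 to 1.22; z = 0.40, one-sided p = 0.34. PFS is negative and OS continues.
- 1.10 at 247 events: 0.86 to 1.41. OS still continues.
- At the first OS look (101 deaths, critical value 3.302), OS futility needs an observed A/B ratio above 0.75 × exp(3.302 × 2/√101) = 1.45.

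**Chance that the PFS rule stops the trial** (25% harm look plus looks at 35% and 65%; independent increments of the log hazard ratio):

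| True PFS HR | Stopped |
|---|---|
| 0.58 | 0.8% |
| 0.65 | 3.2% |
| 0.70 | 7.2% |
| 0.73 | 10.8% |
| 0.80 | 23.4% |
| 1.00 | 71.6% |

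At 0.73 the figure depends on timing: 5.5% with a look at 65% only, 5.2% with one look at 80% or 90%, 7.8% at 65% and 95%, and 12.5-12.7% with a third look at 90-95%. Section 9.2.3 expects analyses 6 to 12 months late. A six-month slip moves the planned months 11.5 and 17.5 to 17.5 and 23.5, which is about 65% and 97% information under the alternative. That points to the lower part of the range.

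**Effect on OS power.** Using the Table 9.2 critical values without futility, OS power is 81.2% at 0.75 and 99.95% at 0.59. The loss cannot exceed the stop probability.
- Planned effects: at least 81.2 − 0.8 = 80.4%, against a stated 80%.
- Phase 2 pair at the planned looks: patient-level simulation gives 88-89%. With looks at 65% and 95%, at least 99.95 − 7.8 = 92%.
- Less favourable pairs at the planned looks: with OS at 0.75, simulated OS power is 72-74% at PFS 0.73, 53-57% at 0.85 and 23-27% at 1.0.

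PFS power at 0.73 is Φ(√(247/4) × ln(1/0.73) − 3.09) = 27%, so OS would indeed be the main route there.

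**What the rule buys.** With no effect and λ = ln 2/median, expected events by month T are 15 × [T − (1 − exp(−λT))/λ].
- 161 PFS events (median 4.1): T = 16.3, with 15 × 16.3 ≈ 244 enrolled and 356 to come. With a delay of 6 to 12 months (about months 22 to 28), the number to come falls to 600 − 15 × 22 = 270 or 600 − 15 × 28 = 180.
- 203 deaths (median 22): T = 34.6, with about 519 enrolled. By then the plan's repeated confidence interval alone has stopped only 14% of trials with no OS effect.

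The PFS rule is therefore the only efficacy-based safeguard likely to act while much of the accrual lies ahead.

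**An alternative for comparison.** Suppose the trial stopped at a PFS look only if the observed OS ratio were also above 1. In simulation, OS power for the phase 2 pair rises to 96-97%, but stopping under no effect by 161 PFS events falls from 71-72% to 48-50%. The added condition would rest on about 22 to 50 deaths. At 22, the standard error of the log ratio is 2/√22 = 0.43, so a true 0.75 appears above 1 with probability 1 − Φ(0.288/0.43) = 25%.

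**The case for a change.** The strongest case for a change is that the rule ends the trial's main test without using any of that test's data, and that the documents offer no rationale. A deliberate PFS gate fits awkwardly with a design meant to succeed on either endpoint, and with Section 9.2, which forgoes early PFS efficacy stopping to protect the OS comparison. The general remark in Section 9.2.3 that the method costs under 1% of power is borne out at 0.58 but says nothing about OS at weaker PFS effects. At the phase 2 pair, almost every stopped trial would otherwise have been positive on OS.

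Much of this stands: the asymmetry exists, it is unexplained, and the losses at weaker PFS effects are real. Three points limit it.

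- The two decision points differ. At 161 PFS events there are only about 50 deaths and much of the accrual lies ahead. At 247 events the planned 360 patients are enrolled and about 101 deaths support a formal OS look. Judging by PFS while survival data are thin, then by OS once they exist, is coherent.
- The costly scenarios are not the ones the plan adopted. Section 1.3.4 calls the phase 2 OS result exploratory, and Section 9.2.2 discounts it to 0.75. The steepest losses need a survival benefit with little or no PFS benefit, for which Section 1.4 offers only a suggestion.
- Keeping OS open is not a one-sentence edit. The first OS look, the OS futility rule and the release of results are all tied to the primary PFS analysis, so each would need a new trigger.

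**Conclusion.** No change follows; this is a fair trade-off. Read plainly, the PFS boundary ends the whole trial, and analysts and the monitoring committee can apply it as written. The plan's figures reproduce. At its own alternative the cost to OS is under one percentage point. At a PFS ratio of 0.73 it stops about 5% to 13% of trials depending on timing, 10.8% at the undelayed looks. Against that, it stops about 72% of null trials before most of the OS information accrues. The alternative examined gives up roughly a third of that protection ((72 − 49)/72 = 32%) to gain power in scenarios outside the planning assumptions. Experienced statisticians could choose either side.

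The stop probabilities assume proportional hazards and the 4/d variance. The simulated OS power figures also assume exponential times and a latent correlation between progression and death of 0 to 0.8, which the documents do not give. The calendar figures assume accrual of 15 patients per month. The judgement would change if the sponsor treated a PFS ratio near 0.73 or weaker, together with a real OS benefit, as the expected case; the plan does not.
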